**Table 1 List of Abbreviations and Definition of Terms**

BSOC	body system organ class
°C	Celsius
CI	confidence interval
CNS	Central Nervous System
CTCAE	Common Terminology Criteria For Adverse Events
eCRF	electronic Case Report Form
EDSS	Expanded Disability Status Scale
ITT	Intent-to-Treat
IRR	Infusion Related Reactions
IV	Intravenous
kg	Kilogram
MedDRA	Medical Dictionary for Regulatory Activities
mg	Milligram
mL	Milliliter
mmHg	Millimeter of Mercury
MS	Multiple Sclerosis
NCI	National Cancer Institute
PPMS	Primary Progressive Multiple Sclerosis
PT	Preferred Term
RMS	Relapsing Multiple Sclerosis
SD	Standard Deviation
U.S.	United States
USPI	United States Package Insert

**Ocrelizumab—Genentech, Inc.**  
**4/Statistical Analysis Plan ML40638**

## 1. **BACKGROUND**

Multiple sclerosis (MS) is a chronic, inflammatory, demyelinating, and degenerative disease of the central nervous system (CNS) that affects approximately 400,000 people in the United States (U.S.) and 2.3 million worldwide (National Multiple Sclerosis Society).

Ocrelizumab is a recombinant humanized monoclonal antibody that selectively targets CD20-expressing B cells (Klein et al. 2013), which are believed to play a critical role in MS. Ocrelizumab is indicated for the treatment of adult patients with relapsing or primary progressive forms of MS (United States Package Insert [USPI]). See the Ocrelizumab Investigator's Brochure for additional details on nonclinical and clinical studies.

According to the currently approved U.S. label, ocrelizumab must be administered at a 600-mg dose through slow intravenous (IV) infusion. The first dose is given as two doses, separated by 14 days, and administered as two 300-mg infusions over the course of 2.5 hours, while subsequent doses are given as a single 600-mg infusion over 3.5 hours.

The most common safety events reported with ocrelizumab are infusion related reactions (IRRs). IRRs occur more frequently during the first infusion of the first dose. The majority of IRRs (>90% of patients reporting IRRs) were of mild to moderate intensity, and the intensity of IRRs decreased with subsequent dosing. Different doses of ocrelizumab have been studied over the years in various patient populations, showing consistently that the proportion of reported IRRs is dose-dependent. However, there is no direct evidence on whether a shorter infusion time would pose an additional safety risk to patients. This study will explore, for the first time, the effect of a shorter infusion on the rate and severity of IRRs.

Refer to the study protocol regarding more details of the study background.

## 2. **STUDY DESIGN**

This study is an open-label, non-randomized study to evaluate rate and severity of IRRs of ocrelizumab infused over a shorter time period than the approved administration rate in patients with Primary Progressive MS (PPMS) or Relapsing MS (RMS) in the U.S.

The study will have 2 cohorts:

- Cohort 1 will examine the effect of administering ocrelizumab per a shorter infusion protocol for Dose 2 or Dose 3 (Week 24 or 48 from the initial infusion). This cohort will consist of patients who have already received one or two doses of ocrelizumab according to the approved infusion protocol (i.e., per current U.S. label) and have reported no serious IRRs and who will then receive the next infusion of ocrelizumab at a higher rate in order to deliver 600 mg over the course of approximately 2 hours.

**Ocrelizumab—Genentech, Inc.**  
**5/Statistical Analysis Plan ML40638**

- Cohort 2 will examine the effect of administering ocrelizumab per a shorter infusion protocol for the second infusion of Dose 1. This cohort will consist of ocrelizumab-naïve patients who, after receiving Infusion 1/Dose 1 of ocrelizumab at the approved rate (300 mg over approximately 2.5 hours or longer) have no reported serious IRRs, will then receive the second 300-mg shorter infusion over approximately 1.5 hours.

All patients will have two safety follow-up telephone calls: the first within 24 hours of the ocrelizumab infusion and the second 30 days after their last ocrelizumab dose.

## **2.1 PROTOCOL SYNOPSIS**

The Protocol Synopsis is in [Appendix 1](#). For additional details, see the Schedule of Assessments in [Appendix 2](#).

## **2.2 OUTCOME MEASURES**

### **2.2.1 Primary Endpoint**

The primary endpoint is the rate and frequency of National Cancer Institute Common Terminology Criteria for Adverse Events, Version 4.0 (NCI CTCAE v4.0) Grade 3 and 4 IRRs in patients who receive the 600 mg shorter infusion.

### **2.2.2 Secondary Endpoints**

The secondary endpoints for this study are as follows:

- Rate and frequency of NCI CTCAE v4.0 Grade 1–4 IRRs in patients who receive the shorter infusion for both cohorts
- Rate and frequency of NCI CTCAE v4.0 Grade 3 and 4 IRRs in patients who receive the 300 mg shorter infusion

### **2.2.3 Safety Outcome Measures**

In addition to IRRs collected as the primary and secondary endpoints, additional safety outcome measures of interest include the number and proportion of patients who require slowing down, interruption, or discontinuation of ocrelizumab due to IRRs following the 300-mg or 600-mg shorter infusion and the following:

- Count and proportion of patients who experienced
  - Treatment-emergent adverse events
  - CTCAE v4.0 Grade 3 to 5 adverse events
  - Serious treatment-emergent adverse events
  - Treatment-emergent adverse events of special interest as applicable
  - Adverse events leading to treatment discontinuation
  - Adverse events leading to withdrawal from study
  - Adverse events leading to infusion adjustment

**Ocrelizumab—Genentech, Inc.**  
6/Statistical Analysis Plan ML40638

- Treatment-related adverse events
- Adverse events with fatal outcome
- Summary of patients who experienced abnormalities (as appropriate), i.e., hepatic function, renal function and hematology values.
- Descriptive statistics (n, mean, standard deviation [SD], median, min, max), including change from baseline analysis, of vital signs -
  - Sitting and supine diastolic blood pressure (mmHg)
  - Sitting and supine systolic blood pressure (mmHg)
  - Pulse rate (beats/minute)
  - Temperature (°C)
  - Weight (kg)

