4.5.4 Vital Signs

Vital signs will include measurements of heart rate, temperature, and systolic and diastolic blood pressure.

Vital signs should be taken approximately 45 minutes prior to premedication. In addition, vital signs should be obtained prior to the ocrelizumab infusion and then approximately every 15 minutes for the first hour, followed by approximately every 30 minutes until 1 hour after the end of the infusion.

Patients will be informed about the possibility of delayed post-infusion symptoms and instructed to contact their study physician if they develop such symptoms.

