5.1.3 Risks Associated with Ocrelizumab

5.1.3.1 Identified Risks and Adverse Drug Reactions

5.1.3.1.1 Infusion-Related Reactions

All CD20+ depleting agents administered via the intravenous route, including ocrelizumab, have been associated with acute IRRs. Symptoms of IRRs may occur during any ocrelizumab infusion, but have been more frequently reported during the first infusion. Physicians should alert patients that IRRs can occur within 24 hours of the infusion. These reactions may present as pruritus, rash, urticaria, erythema, throat irritation, oropharyngeal pain, dyspnea, pharyngeal or laryngeal edema, flushing, hypotension, pyrexia, fatigue, headache, dizziness, nausea, and tachycardia.

Patients should be observed for at least one hour after the completion of the infusion for any symptom of IRR. They will be informed about the possibility of delayed post-infusion symptoms and instructed to contact their study physician if they develop such symptoms.

Hypotension, as a symptom of IRR, may occur during ocrelizumab infusions. Therefore, withholding of antihypertensive treatments should be considered for 12 hours prior to and throughout each ocrelizumab infusion.

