Review inclusion and exclusion criteria	x			
Physical examination ^e	x			
Vital signs ^f		x		
EDSS	(x) ^g			
Hematology	x			
Pregnancy test ^h		x		
Adverse event assessment ⁱ			x	x
Concomitant treatment review	x	x		x ^j
Methylprednisolone and antihistamine premedication ^k		x		
Ocrelizumab administration		x ^l		

eCRF=electronic Case Report Form; EDSS=Expanded Disability Status Scale; IRR=infusion-related reaction; IV=intravenous.

^a Day 1 may occur at Week 24 or 48, depending on the previous treatment cycle.

^b Patients who receive ocrelizumab in this study or who discontinue from treatment or the study early, should enter the Safety Follow-up Period and be assessed 30 days counting from the date of their last ocrelizumab infusion via telephone.

^c Written informed consent will be obtained from all patients in order to be eligible for the study and prior to any study procedures.

^d Medical history includes clinically significant diseases, surgeries, reproductive status, smoking history, and all medications (e.g., prescription drugs, over-the-counter drugs, herbal or homeopathic remedies, and nutritional supplements) used by the patient within 4 weeks prior to the visit. Demographic data will include age, sex, and self-reported race/ethnicity.

^e A physical examination may be conducted, per standard of care. Any abnormality identified should be recorded on the eCRF. New or worsened clinically significant abnormalities should be recorded as adverse events, if appropriate.

Appendix 1 (cont.) Schedule of Activities: Cohort 1

- ^f Vital signs will include the measurements of heart rate, systolic and diastolic blood pressures, and temperature. Vital signs should be taken approximately 45 minutes prior to the premedication methylprednisolone infusion. In addition, vital signs should be obtained prior to the ocrelizumab infusion then approximately every 15 minutes for the first hour, followed by approximately every 30 minutes until 1 hour after the end of the infusion.
- ^g EDSS does not need to be performed if results within 6 months are available.
- ^h On infusion visits, a urine pregnancy test must be performed prior to premedication in all women of childbearing potential. If a urine pregnancy test is positive, it must be confirmed by a serum pregnancy test. Ocrelizumab must be withheld until pregnancy status is confirmed.

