### **4.3.1 Demographics and Baseline Characteristics**

The following patient demographics and baseline characteristics will be summarized for the ITT population:

- Age (years)
- Age (years) group: (age categories  $\leq 40$ ,  $> 40$ , and age categories  $\geq 18$ -  $<40$ ,  $\geq 40$ - $\leq 55$ )
- Sex
- Self-reported race and ethnicity
- Baseline weight
- EDSS score
- EDSS category: (EDSS categories  $< 4$ ,  $\geq 4$ , and EDSS categories  $< 2.5$ ,  $\geq 2.5$ )
- Female fertility status
- MS type (RMS, PPMS)

Demographics and baseline characteristics will be summarized further by MS diagnosis categories (RMS, PPMS).

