#### **4.6.4        Vital Signs**

Baseline, post-baseline, and change from baseline in vital signs will be summarized. Baseline for vital signs is defined as the last measurement prior to pre-infusion medication at Day 1 for both cohort 1 and cohort 2.

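### The SAP's vital-sign list includes posture and weight rows with no scheduled source, and its group summaries do not count patients whose measured changes go unreported

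*SAP*

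**What the plan says.** SAP 2.2.3 (Safety Outcome Measures) asks for "Descriptive statistics (n, mean, standard deviation [SD], median, min, max), including change from baseline analysis, of vital signs". The items listed are "Sitting and supine diastolic blood pressure (mmHg"), "Sitting and supine systolic blood pressure (mmHg"), pulse rate, temperature and weight. SAP 4.3.1 adds "Baseline weight" to the baseline table. SAP 4.6.4 says: "Baseline, post-baseline, and change from baseline in vital signs will be summarized". It sets baseline as the last value before premedication on Day 1, for both cohorts.

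Protocol 4.5.4 says: "Vital signs will include measurements of heart rate, temperature, and systolic and diastolic blood pressure". The schedules in Protocol Appendices 1 and 2 agree: "Vital signs will include the measurements of heart rate, systolic and diastolic blood pressures, and temperature". The SAP reprints both schedules in its own appendices with the same short list.

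Readings are due about 45 minutes before premedication and again before ocrelizumab. After that they are due about every 15 minutes for the first hour, then about every 30 minutes until 1 hour after the infusion ends.

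Protocol 5.1.3.1.1 includes among the possible presentations of an IRR "hypotension, pyrexia, fatigue, headache, dizziness, nausea, and tachycardia".

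**The concern.** There are two separate points.

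First, the SAP promises rows that the scheduled data cannot fill. A sitting and supine split needs posture to be recorded, and a weight change needs two weights. The protocol schedules neither.

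Second, the useful information in repeated readings during an infusion is at patient level: who had a marked transient change, and how many did. A mean at a reading dilutes a few large changes across the whole cohort, and a minimum or maximum shows only the single most extreme value. The SAP plans no worst value per patient, no limit, no count and no vital-sign listing.

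This matters because the study is open-label with no control arm. An abnormal reading becomes an adverse event only through the criteria in Protocol 5.3.5.6, one of which is the investigator's judgment of clinical significance. The scheduled readings are a check on pressure, heart rate and temperature that does not pass through that reporting step, and the planned tables make little use of it.

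**Working it through.** **1. The lists side by side**

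| Item | SAP 2.2.3 | Protocol 4.5.4 and both schedules |
|---|---|---|
| Heart or pulse rate | yes | yes |
| Temperature | yes | yes |
| Systolic and diastolic pressure | sitting and supine | one pressure, posture not stated |
| Weight | yes, with change | not listed |

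Weight is also absent from the demographic data (Protocol 4.5.2) and is not named in the physical examination (Protocol 4.5.3), which is a screening item only. Both contacts after the infusion visit are telephone calls, so no later visit could supply a second weight.

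**2. How much data the summaries cover**

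At the nominal durations in Protocol Tables 2 and 3 (120 and 90 minutes), the readings after infusion start are:

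- Cohort 1: 15, 30, 45, 60, 90, 120, 150 and 180 minutes = 8
- Cohort 2: 15, 30, 45, 60, 90, 120 and 150 minutes = 7

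Two readings before ocrelizumab come on top. With 100 and 50 patients, this is 100 × 8 + 50 × 7 = 1,150 scheduled reading times after infusion start. SAP 4.6.4 does not say whether post-baseline values are summarized at each time or pooled.

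**3. The plan's own interval method**

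Clopper-Pearson limits are: lower = Beta quantile(0.025; x, n − x + 1), upper = Beta quantile(0.975; x + 1, n − x). All 27 rows of SAP Table 2 reproduce to the printed decimals (largest difference 0.005 percentage points).

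**4. What a mean would show (illustration)**

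The documents give no SD for vital signs and no expected frequency of falls. Assumed here: k of n patients fall by d mmHg at the same reading, with an SD of change between 8 and 15 mmHg. Then shift in mean = k × d / n, and SE = SD / √n.

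| Cohort | k of n | d (mmHg) | Shift in mean (mmHg) | SE (mmHg) |
|---|---|---|---|---|
| 1 | 2 of 100 | 20 to 40 | 0.4 to 0.8 | 0.8 to 1.5 |
| 1 | 5 of 100 | 20 to 40 | 1.0 to 2.0 | 0.8 to 1.5 |
| 2 | 3 of 50 | 20 to 40 | 1.2 to 2.4 | 1.1 to 2.1 |

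If five 40 mmHg falls in Cohort 1 are spread evenly over the 8 readings, each mean moves by 5 × 40 / 100 / 8 = 0.25 mmHg. The minimum change would show that at least one patient had a large fall. Extreme minima at several readings would not show whether they came from one patient or several.

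**5. What a count would show**

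With the plan's exact method and illustrative counts:

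| Cohort | Patients beyond a limit | Proportion | Exact 95% CI |
|---|---|---|---|
| 1 | 0 of 100 | 0% | 0 to 3.62% |
| 1 | 2 of 100 | 2% | 0.24 to 7.04% |
| 1 | 5 of 100 | 5% | 1.64 to 11.28% |
| 2 | 0 of 50 | 0% | 0 to 7.11% |
| 2 | 3 of 50 | 6% | 1.25 to 16.55% |

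**6. The baseline**

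SAP 4.6.4 places the vital-sign baseline on Day 1 for both cohorts. In the Cohort 2 schedule the only visit with vital signs is Day 15, and the note to Protocol Figure 2 describes Day 1 of Dose 1 as standard of care. Read literally, Cohort 2 has no scheduled baseline reading from which to compute a change.

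**The case against.** The strongest reply is that patients with these signs are already counted elsewhere. Protocol 5.3.5.6 requires an abnormal vital sign to be reported as an adverse event if it is symptomatic, changes study treatment, leads to an intervention or a change in concomitant therapy, or is judged clinically significant. Protocol 5.3.5.1 sends IRR signs and symptoms to a dedicated form, and SAP 4.6.2 codes them and summarizes them by preferred term. Adverse events are recorded whatever their cause (Protocol 5.2.1), so hypotension, tachycardia or fever judged unrelated is still tabulated. Patients whose infusion is slowed, interrupted or stopped for an IRR are counted with exact intervals. All of this stands, and it confines the gap to measured changes that no one reports, such as an asymptomatic fall judged not significant.

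Three further replies have weight.

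- SD, median, minimum and maximum are planned as well as the mean, so the tables are not blind to extremes. They still do not give a number of patients.
- The 40 mmHg fall is a hypothetical figure, and a fall that large is among the likeliest to be reported. The lower end of the range is closer to what could be missed.
- A baseline before premedication is a legitimate choice and matches a scheduled reading. The SAP does not say how it classifies the later reading before ocrelizumab. The case for also showing change from that reading is that it would help separate infusion effects from premedication effects. It does not rest on the chosen baseline being wrong.

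**Conclusion.** The point holds in limited form. The posture split and the weight change have no scheduled source, and baseline weight has none either. For the signs that are collected, no planned vital-sign statistic gives the number of patients with a transient abnormality. The practical loss is confined to unreported measured changes. Its size cannot be calculated from the documents, and the mean shifts of 0.4 to 2.4 mmHg shown above rest on assumed falls, frequencies and SDs.

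A reader might infer that the study cannot say how many patients had hypotension, tachycardia or fever. The documents do not support that, because the adverse-event and IRR-symptom tables count the reported cases regardless of causality. A reader might also infer that blood pressure is not measured. It is measured; only the posture is unspecified. The case report form is not among the documents, so a site could record a weight, but the protocol does not ask for one.

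The primary and secondary endpoints are unaffected. Removing the unobtainable rows would change no result by itself. The gain comes from a better summary of readings that are already scheduled.

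**What to change.** Amend the SAP as follows.

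- **2.2.3:** match the list to Protocol 4.5.4 by removing the posture split and the weight change. In 4.3.1, name the source of baseline weight or drop it.
- **4.6.4, worst values:** for each patient and by cohort, derive the lowest systolic and diastolic pressure and the highest heart rate and temperature from infusion start to 1 hour after its end. Report the number and proportion of patients beyond limits that the sponsor writes into the SAP in advance, with exact Clopper-Pearson intervals. No vital-sign limits appear in the documents at present; the mention of marked abnormalities in Protocol 6.5 follows a sentence on laboratory parameters.
- **4.6.4, change:** report change from the scheduled pre-ocrelizumab reading alongside change from the pre-premedication baseline.
- **4.6.4, baseline day:** reconcile Day 1 for both cohorts with the Day 15 treatment visit in the Cohort 2 schedule.

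The cost is SAP wording, one more descriptive table, and the work of fixing limits beforehand. No new data collection is needed.

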### **2.3 DETERMINATION OF SAMPLE SIZE**

This study will enroll approximately 150 patients, with 100 from Cohort 1 and 50 from Cohort 2.

Based on the sample size of 100 patients in Cohort 1 and 50 patients in Cohort 2, the 95% confidence intervals (CIs) for some assumed Grade 3 or 4 IRRs are provided in the table below.

**Table 2 Determination of Sample Size**

Sample Size	Number of Pts with Grade 3 or 4 IRRs	IRR Rate (%)	Exact LCL (%)	Exact UCL (%)
50	1	2	0.05	10.65
50	2	4	0.49	13.71
50	3	6	1.25	16.55
50	4	8	2.22	19.23
50	5	10	3.33	21.81
50	6	12	4.53	24.31
50	7	14	5.82	26.74
50	8	16	7.17	29.11
50	9	18	8.58	31.44
100	1	1	0.03	5.45
100	2	2	0.24	7.04
100	3	3	0.62	8.52
100	4	4	1.10	9.93
100	5	5	1.64	11.28
100	6	6	2.23	12.60
100	7	7	2.86	13.89
100	8	8	3.52	15.16
100	9	9	4.20	16.40
150	1	0.67	0.02	3.66
150	2	1.33	0.16	4.73
150	3	2	0.41	5.73
150	4	2.67	0.73	6.69
150	5	3.33	1.09	7.61
150	6	4	1.48	8.50
150	7	4.67	1.90	9.38
150	8	5.33	2.33	10.24
150	9	6	2.78	11.08

Pts=Patients; IRR=infusion-related reaction; LCL=lower confidence limit; UCL=upper confidence limit based on 95% confidence interval.

## 2.4 ANALYSIS TIMING

The first 50 patients in cohort 1 were summarized for baseline characteristics and presented at the 2019 American Academy of Neurology (AAN) and Consortium of Multiple Sclerosis Centers (CMSC) 2019 congresses.

**Ocrelizumab—Genentech, Inc.**  
8/Statistical Analysis Plan ML40638

Final analysis will be conducted when all planned 150 patients (100 patients from Cohort 1 and 50 patients from Cohort 2, respectively) have completed the 30-day follow-up after the study drug administration and the database is cleaned and locked.

Regular safety reviews will be conducted by Data Management and the sponsor.

### **3. STUDY CONDUCT**

#### **3.1 RANDOMIZATION ISSUES**

Not applicable.

### **4. STATISTICAL METHODS**

This study is designed to evaluate the safety (i.e. IRRs) of ocrelizumab administered over a shorter time period than the approved administration rate in patients with PPMS or RMS in the U.S. No efficacy outcome is collected in this study.

Descriptive statistics, i.e. frequency and proportion of patients, will be used to summarize the incidence of IRR events and potential incidence of modifications (i.e. slowing, interruption, or discontinuation) to the study drug following IRRs in respective study cohorts. When applicable, 95% confidence intervals (CIs) will be provided using exact Clopper-Pearson method for the proportion to quantify the uncertainty of the observed value.

#### **4.1 ANALYSIS POPULATIONS**

Based on the study design and objectives, all safety analyses and exposure summaries will be performed using the safety population. Demographic, baseline characteristics, and patient disposition will be summarized using intent-to-treat (ITT) population.

##### **4.1.1 Intent-to-Treat Population**

All enrolled patients will be included in the ITT population. Patients who prematurely withdrew from the study for any reason and who did not have any assessments for any reason will still be included in the ITT population.

##### **4.1.2 Safety Population**

The safety population is defined as all enrolled patients who received any dose of study treatment, even if the infusion was incomplete.

